### **9.8.3 Safety Laboratory Variables**

Clinical laboratory variables will be presented by using both summary statistics.

## **10 DATA HANDLING**

### **10.1 Source Data and Source Documents**

#### **Source Data – International Conference on Harmonisation (ICH) Definition**

Source data are defined as all information in original records and certified copies of original records of clinical findings, observations, or other activities in a clinical trial necessary for the reconstruction and evaluation of the trial. Source data are contained in source documents (original records or certified copies).

#### **Source Documents - ICH Definition**

Source documents are defined as original documents, data, and records (e.g. hospital records, clinical and office charts, laboratory notes, memoranda, patients' diaries or evaluation checklists, pharmacy dispensing records, recorded data from automated instruments, copies or transcriptions certified after verification as being accurate copies, microfiches, photographic negatives, microfilm or magnetic media, x-rays, patient files, and records kept at the pharmacy, at the laboratories and at medico-technical departments involved in the clinical trial).

#### **Trial-specific Source Data Requirements**

For each patient allocated to treatment, the Investigator will indicate in the hospital/medical source records that the patient participates in this trial and the date of obtaining the informed consent. The records should document data on the condition of the patient at the time the patient is enrolled in the trial to enable verification of eligibility. Signed and dated informed consent will be stored and archived according to local requirements. In addition the following information, at the minimum, will also be recorded in the hospital/medical source records for each patient:

- Documentation of signed and dated Informed Consent
- Patient's name and date of birth
- Screening/randomisation number
- Body weight and height
- Dosing of IMP – date of first and last dose
- Occurrence of any adverse events/SAEs (including description and duration)
- Medical history
- Date of UC diagnosis
- Date of each visit
- Any assessment performed
- Any concomitant therapy
- Status of the patient at the end of trial

- Reason for discontinuation/withdrawal, if applicable

The following documents collected during the trial should be stored and archived together with the patient's hospital/medical records or in the Investigator File as agreed upon prior to the trial start at each trial site:

- Laboratory print-outs from central and local laboratory – evaluated, signed, and dated by the Investigator or a delegated Sub-Investigator
- ECG print-outs/reports – evaluated, signed, and dated by the Investigator or a delegated Sub-Investigator
- Patient dispensing logs of IMP
- Evaluations of physical examinations
- Collection of laboratory samples
- Demographics

For withdrawals, all available e-CRF data should be monitored and source data verified. Source data verification (SDV) will be handled the same way for withdrawn patients as for completed patients.

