### 3.4.3 Blinding

A central, computer-based randomisation procedure is used to eliminate selection bias. To reduce the risk of breaking the blind, IMP thawing and reconstitution will be carried out at the trial site by blinded site personnel, independent of the Investigator and the Sponsor. The appearance of the reconstituted IMP, as well as the infusion volume (290 mL) will be identical for all treatment groups.

In order to reduce bias as much as possible, the trial is double-blind, keeping all subjects and the investigator blinded to the treatment. The randomisation list will not be available to any person involved in the conduct and evaluation of the trial until the trial database is locked.

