## 5.5 Blinding/Unblinding

### 5.5.1 Blinding

In order to reduce bias as much as possible, the trial is double-blind, keeping all subjects, the Investigator, and all staff involved in the conduct of the trial blinded to the treatment administered.

Patients will be centrally, dynamically randomised using Interactive Web Response System (IWRS). The randomisation list will not be available to any person involved in the conduct (Section 5.1) and the scientists analysing blood samples for TJ301 (Section 3.4.3), and evaluation of the trial until the trial database is locked.

The bioanalytical laboratory staff is authorized to receive the randomization list prior to the study conclusion to determine which samples should be analyzed for TJ301 according to standard operating procedures.

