### **7.1.4 Clinical Safety Laboratory Parameters**

Laboratory parameters: urinalysis (dipstick), urine pregnancy test, urine drug panel, haematology, clinical chemistry, coagulation, serum pregnancy test, TB, HIV, HBV, HCV, EBV, and CMV infection test, Clostridium difficile assay, erythrocyte sedimentation rate [ESR], C-reactive protein (CRP), neutrophil and platelet count, and biopsy samples ([Appendix 2](#)) will be measured at local sites according to the schedule in [Table 1](#).

Anti-TJ301 antibodies, Pharmacokinetics TJ 301, IL-6, IL-6/sIL-6R complex, and faecal calprotectin tests will be analysed in central lab; sample collection methods and handling procedures will be described in a separate laboratory manual.

The Investigator will review the laboratory results and evaluate and document whether the results are normal or abnormal and whether abnormal results are non-clinically significant or clinically significant. Pre-existing clinically significant conditions diagnosed as a result of the screening procedures must be recorded as medical history. If any clinically significant abnormal findings are discovered after informed consent or any pre-existing conditions worsen during the trial, these must be recorded as adverse events. The laboratory report will be signed and dated by the Investigator.

For female subjects, a serum  $\beta$ -HCG and a serum pregnancy test will be conducted at the Screening Visit (Visit 1) and urine pregnancy tests will be conducted at visit 8 and Follow-up visit.

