## **7.5 Handling of Biological Samples**

A central laboratory will be used in this trial for Anti-TJ301 antibodies, TJ 301 PK, IL-6, IL-6/sIL-6R complex, and faecal calprotectin tests. Sampling tubes, material for shipment of the samples, and a laboratory manual detailing all sample collection and shipment procedures will be provided and distributed to the trial sites by the central laboratory.

Except for PK subgroup patients, the total amount of blood planned to be collected from each patient who will be enrolled during the course of the trial is approximately 200 mL.

For PK subgroup, the total amount of blood planned to be collected from each patient during the course of the trial is approximately 300 mL.

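### Section 10.1 has the Investigator evaluate and sign central-laboratory print-outs, which can carry only drug-level, antibody and biomarker results, and the protocol states no rule keeping these results from sites

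*Protocol*

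**What the plan says.** Section 10.1, under the trial-specific source data requirements, opens a list with "The following documents collected during the trial should be stored and archived together with the patient's hospital/medical records" (or in the Investigator File). Its first item is "Laboratory print-outs from central and local laboratory – evaluated, signed, and dated by the Investigator or a delegated Sub-Investigator".

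Section 7.5 defines what the central laboratory does: "A central laboratory will be used in this trial for Anti-TJ301 antibodies, TJ 301 PK, IL-6, IL-6/sIL-6R complex, and faecal calprotectin tests". Section 7.1.4 and Appendix 2 give the same five items and assign the routine safety tests, ESR, CRP, and neutrophil and platelet counts to local sites.

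Section 7.1.4 names the central assays and then continues: "The Investigator will review the laboratory results and evaluate and document whether the results are normal or abnormal". It adds: "The laboratory report will be signed and dated by the Investigator".

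On blinding, Section 3.4.3 promises "keeping all subjects and the investigator blinded to the treatment", and Section 5.5.1 promises "keeping all subjects, the Investigator, and all staff involved in the conduct of the trial blinded to the treatment administered". The safeguard both sections spell out is restricted access to the randomisation list.

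**The concern.** A signature duty on laboratory print-outs is routine when the central laboratory runs safety tests. Here it runs none. The word 'central' in Section 10.1 can refer only to the drug concentration, antibodies to the drug, IL-6, the complex the drug binds, and calprotectin. A site that follows the instruction as written will ask for these reports and have the Investigator or a Sub-Investigator read them.

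At stake is the blind of the people who make the trial's subjective judgements. The PGA is the main one, because it enters the primary endpoint and is recorded at the site. The Investigator also judges adverse-event causality and has discretion over corticosteroid tapering (Section 4.3.3). The print-outs would sit in site records that the Monitor, a Sponsor representative (Section 5.6.1), checks under full source data verification (Section 11.1), so exposure need not stop at the site.

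**Working it through.** The plan states no figure on this point, so the check sets passages side by side and then counts the patients exposed.

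1. **Duty.** Section 10.1 covers central and local print-outs alike and exempts no assay.

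2. **What a central print-out can contain.** Sections 7.1.4 and 7.5 and Appendix 2 agree on five items: TJ301, anti-TJ301 antibodies, IL-6, IL-6/sIL-6R complex and calprotectin. There is no central safety panel to which the duty could harmlessly apply.

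3. **Firewall.** Sections 3.4.3 and 5.5.1 restrict the randomisation list. No section of the protocol withholds, masks or delays assay results. Section 10.4 leaves transfer timing and data access to data management documents, and Section 7.1.4 leaves sample collection and handling to a laboratory manual. Neither is shown.

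4. **Which result reveals the arm.** Assuming an assay that detects the drug, a measurable TJ301 level shows active treatment and its absence at the end of an infusion shows placebo. Section 5.5.1 also lets bioanalytical staff use the randomisation list to choose which samples are assayed for TJ301, so even the existence of a result could be informative. Antibody and complex results may hint at treatment but do not establish it.

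5. **Timing.** PK sampling starts with the first dose on Day 0 (Section 6.2.5); the primary endpoint is assessed at Week 12. The protocol gives no reporting times, so how early a result could reach a site is unknown.

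6. **Patients exposed to the decisive result.** Section 6.2.5 gives 8 PK patients per arm in three arms.
 - PK subgroup: 3 × 8 = 24, and 24/90 = 26.7%.
 - On active drug: 2 × 8 = 16, and 16/90 = 17.8%.
 - Section 9.6.3 speaks of peak and trough concentrations in all patients, but the Table 1 footnote limits PK sampling to the Mainland China subgroup. I use 24.
 - Antibody and biomarker samples are scheduled for all 90 patients.

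7. **Route to the primary endpoint.** Remission needs a full Mayo score of at most 2, no subscore above 1 and bleeding 0. Take bleeding 0, stool frequency 1 and endoscopy 1. With PGA 0 the total is 0 + 1 + 1 + 0 = 2, which is remission. With PGA 1 it is 0 + 1 + 1 + 1 = 3, which is not. So the PGA alone can decide the outcome. This is one example, not a complete map, because stool and bleeding scores are diary averages (Section 7.1.1) and need not be whole numbers. Section 7.1.1 provides blinded central readers for endoscopy and describes no independent rater for the PGA.

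**The case against.** The strongest reply is that Section 10.1 is an archiving list. Its reference to the period of the trial qualifies the collection of documents; it does not say that TJ301 concentrations are reported to sites, or when. Section 5.5.1 is the specific rule on blinding and should prevail, and release of results may be settled in the data management documents (Section 10.4) or the laboratory manual. Section 7.1.4 sits under safety parameters and asks whether results are normal, abnormal or clinically significant, which fits the local tests; the protocol gives no normal range for a drug concentration. Nor does it say that the person who signs is the person who scores the PGA.

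Much of this stands. In-trial release is a risk that the wording creates, not an event it describes, and the review rule in Section 7.1.4 is most naturally read as covering safety tests. What does not fall away is the express signature duty on central print-outs. A withholding rule in another document would leave that instruction in conflict with it, and the protocol describes no separation between the signatory and the PGA rater.

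A reader might infer that all 90 patients would be unblinded. The documents do not support that: only the TJ301 concentration is decisive, and Table 1 confines it to the PK subgroup. A reader might also be tempted to convert changed PGA scores in a few PK patients into a shift in the remission rate. Nothing in the documents says how many scores would change, so such a figure would be invented. Other routes to bias are partly protected: endoscopy is verified by blinded central readers, and withdrawal for worsening rests on a diary-based bleeding increase with endoscopic confirmation.

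**Conclusion.** The point holds as a conflict on literal reading: an affirmative instruction to evaluate and sign central-laboratory print-outs, set against a promise to keep the Investigator blinded, with no withholding rule in the protocol to reconcile them. The decisive exposure is 24 of 90 patients, 16 on active drug. This rests on Table 1 governing PK sampling and on the assay distinguishing drug from none. Knowledge of the arm could bias the PGA and through it the primary endpoint; the size of any bias cannot be estimated from the documents. The conclusion is not that sites will be unblinded, since the unseen laboratory manual and data management documents may withhold the results.

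**What to change.** In Section 10.1, and for clarity in Section 7.1.4, limit Investigator evaluation and signature to local safety laboratory results. Add a rule to this effect:

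*Central-laboratory results (TJ301 concentration, anti-TJ301 antibodies, IL-6, IL-6/sIL-6R complex and faecal calprotectin) are not released to site staff or to blinded sponsor staff, including monitors, until database lock, except through the emergency unblinding procedure in Section 5.5.2. Access by the Safety Review Committee is governed by its charter.*

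Calprotectin is included for consistency, so that no central result is left neither reviewed nor withheld. Repeat the rule in the laboratory manual and the data management plan.

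The cost is wording in two sections and a reporting instruction to the central laboratory. The downside is that sites do not see these results during the trial; none of them is used for eligibility or for a stated safety decision. The change does not remove every clue: neutrophil and platelet counts, which Section 8.3 links to IL-6 inhibition, stay visible to sites as safety tests.

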## **10.2 Electronic Case Record Form**

An e-CRF system provided by an independent third-party CRO will be used for data capture. The system is validated and access at all levels to the system is granted/revoked following the Sponsor's procedures, in accordance with regulatory and system requirements.

Data should be entered into the system timely after the patient has attended a visit or after the data become available, as applicable.

The Investigator will approve/authorise the e-CRF entries for each patient with an electronic signature which is equivalent to a handwritten signature.

The e-CRF system and the database will be hosted at the independent third party CRO. After the trial database is declared clean and released to the statistician, a final copy of the database will be stored at the Sponsor. The Investigator will also receive a copy of the trial site's final and locked data (including audit trail, electronic signature and queries) as write-protected PDF-files produced by the independent third party CRO. The PDF-files will be stored on a CD and will be provided to the Investigator before access to the e-CRF is revoked.

Errors occurring in the e-CRF will be corrected electronically. Such corrections/modifications will be automatically tracked by an audit trail detailing the date and time of the correction and the name of the person making the correction.

### **10.3 Use of Patient Reported Outcome Instruments**

A Paper Diary will be used by the patients for the reporting of daily bowel movement frequency and rectal bleeding (blood in stool) for the calculation of Mayo score at each visit. Patients will be instructed on the use of the Paper Diary. This will include symptom reporting (stool frequency, blood in stool) throughout the trial. The Paper Diary should be completed by the patient every evening starting the evening of the day of Visit 1. A separate manual on the use of the system will be provided to each investigational site.

### **10.4 Data Management**

A set of data management documents will be created under the responsibility of the Sponsor or CRO. The data management plan will be issued before data collection begins and will describe all functions, processes, and specifications for data collection, cleaning and validation.

The data management documents will describe captured methods, who is authorised to enter the data, decisions about ownership of data, source data storage, which data will be transferred (including timing of transfers), the origin and destination of the data and who will have access to the data at all times.

### **10.5 Provision of Additional Information**

On request, the Investigator will provide the Sponsor and CRO with additional data relating to the trial, duly anonymised and protected in accordance with applicable requirements.

## **11 MONITORING PROCEDURES**

### **11.1 Periodic Monitoring**

The Monitor will contact and visit the Investigator periodically to ensure adherence to the Protocol, International Conference on Harmonisation (ICH)-Good Clinical Practice (GCP), standard operating procedures and applicable regulatory requirements, maintenance of trial-related source records, completeness, accuracy, and verifiability of e-CRF entries compared to source data. The Investigator will permit the Monitor direct access to all source data, including medical records, and/or documents in order to facilitate data verification. The Investigator will co-operate with the Monitor to ensure that any discrepancies that may be identified as resolved. The Investigator is expected to be able to meet the Monitor during these visits. When the first patient is allocated to treatment at the trial site, a monitoring visit will take place shortly afterwards. For this trial, the frequency of the monitoring visits is intended to be approximately every 6-8 weeks. Frequent monitoring is expected when new patients have been included; thereafter there may be longer intervals between the visits. The frequency of monitoring is also dependent on the number of patients at each trial site.

One hundred percent SDV will be performed. The SDV process and definition of key variables to be monitored will be described in detail in the Monitor's Plan for the trial.

### **11.2 Audit and Inspection**

The Investigator will make all the trial-related source data and records available at any time to quality assurance auditor(s) mandated by the Sponsor, or CRO, or to domestic/foreign regulatory inspectors or representatives from IECs who may audit/inspect the trial.

The main purposes of an audit or inspection are to assess compliance with the trial protocol and the principles of ICH-GCP including the Declaration of Helsinki and all other relevant regulations.

The patients must be informed by the Investigator and in the Informed Consent Documents that authorised Sponsor representatives and representatives from regulatory authorities and IECs may wish to inspect their medical records. During audits/inspections the auditors/inspectors may copy relevant parts of the medical records. No personal identification apart from the screening/randomisation number will appear on these copies.

The Investigator should notify the Sponsor without any delay of any inspection by a regulatory authority or IEC.

### **11.3 Confidentiality of Patient Data**

The Investigator will ensure that the confidentiality of the patients' data will be preserved. In the e-CRF or any other documents submitted to the Sponsor, the patients will not be identified by their names, but by an identification system, which consists of an assigned number in the trial. Documents that are not for submission to the Sponsor (e.g. the confidential patient identification

code and the signed Informed Consent forms), will be maintained by the Investigator in strict confidence.

## **12 CHANGES IN THE CONDUCT OF THE TRIAL**

### **12.1 Protocol Amendments**

Any change to this Protocol will be documented in a Protocol Amendment, issued by the Sponsor or CRO, and agreed upon by the Investigator and the Sponsor prior to its implementation.

Protocol amendments will be submitted for notification of IECs and Regulatory authorities, in accordance with local regulations. An approval by the IECs is required for a substantial amendment, e.g. one which could affect the safety of the patients, or which entails a change to the scope/design of the trial.

Changes to the protocol to eliminate immediate hazard(s) to trial patients may be implemented prior to IEC approval.

### **12.2 Deviations from the Protocol**

Deviations from the Protocol should not occur. If deviations occur, the Investigator must inform the Monitor, and the implications of the deviation must be reviewed and discussed. Any deviation must be documented (or included in e-CRF data). In addition, a set of deviations must be accompanied by a description of the deviation, the relevant dates (start and stop), and the action taken. A Log of Protocol Deviation Reports will be maintained by the Sponsor or CRO. Deviation reports and supporting documentation must be kept in the Investigator's File and in the Trial Master File.

### **12.3 Premature Trial Termination**

Both the Investigator (with regard to his/her participation) and the Sponsor reserve the right to terminate the trial at any time. Should this become necessary, the procedures will be agreed upon after consultation between the two parties. In terminating the trial, the Sponsor and the Investigator will ensure that adequate consideration is given to the protection of the best interests of the patients. Regulatory authorities and IECs will be informed.

In addition, the Sponsor reserves the right to terminate the participation of individual trial sites. Conditions that may warrant termination include, but are not limited to, insufficient adherence to protocol requirements and failure to enter patients at an acceptable rate.

## **13 REPORTING AND PUBLICATION**

### **13.1 Clinical Trial Report**

The data and information collected during this trial will be reported in a clinical trial report prepared by the Sponsor or CRO and submitted for comments and signature to the Investigator.

### **13.2 Confidentiality and Ownership of Trial Data**

Any confidential information relating to the IMP or the trial, including any data and results from the trial will be the exclusive property of the Sponsor. The Investigator and any other persons involved in the trial will protect the confidentiality of this proprietary information belonging to the Sponsor.

